### **7.2. Statistical Methods**

The primary analysis is an intent-to treat analysis of all randomised patients. Patients will be analysed according to the treatment group to which they were randomised, irrespective of which study drug was given or if any study drug was received. Additional populations like a per protocol population may be defined in the statistical analysis plan

The difference in relapse-free survival will be compared between the two treatment groups by means of a Cox proportional hazards model stratified for time since diagnosis (3 strata: 0, 6 or 12 months ago). It will be verified whether the treatment effect is stratum dependent. If so, the strata will be analysed separately. Furthermore, using a Cox proportional hazards model it will be investigated whether the potential treatment effect is different for VDR immunoreactivity and genetic variability in the Vitamin D pathway. A correction for other baseline covariates like gender, age and

baseline Vitamin D level will be performed as sensitivity analyses. No interim analysis for efficacy is foreseen. Potential subgroups analysis like for instance calcium serum levels will be defined in the statistical analysis plan

The evolution in 25(OH)D3 levels in function of genetic variability in the Vitamin D pathway will be analysed by a linear mixed model. Sensitivity analyses will include patient's compliance, seasonal effects and patient's baseline characteristics like age and gender.

In order to examine the effect of the actual 25(OH)D3 levels rather than just supplementation, the evolution of 25(OH)D3 levels and relapse-free survival will be jointly modelled.

The potential correlation between VDR immunoreactivity and stage at diagnosis will be assessed by means of a Kruskal Wallice test.

The potential correlation between vitamin D levels at diagnosis with melanoma site and melanoma subtype will be assessed by means of an analysis of variance. This analysis can only be performed for newly diagnosed patients because vitamin D levels at diagnosis will not be available for patients who had their diagnosis 6 or 12 months ago.

Full details of the statistical analyses will be described in a statistical analysis plan which will be finalized before database lock.

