NMM are less frequent, occur mostly in males and are the most aggressive form, since they show a vertical growth phase from the beginning. They present themselves as rapid growing black often ulcerated tumors. LMM arises in a long standing pigmented precursor lesion and is located on chronic photodamaged skin. ALMM appear on palms and soles initially as flat pigmented lesions resembling moles, which start to increase in size and ultimately develop irregular areas of pigmentation. Subungual melanomas are most often located on the thumb nail of the great toe and present themselves as a narrow pigmented band, which slowly widens and ultimately produces a subungual mass. Different risk factors are associated with different subtypes of CMM and different locations of malignant melanoma: while chronic photodamage preferentially associates with LMM and malignant melanoma on head and neck region, a high count of naevi preferentially associates with malignant melanoma on the trunk, indicating that different pathways may lead to the development of malignant melanoma, i.e. a pathway through chronic sun exposure, and a melanomagenetic pathway (Whiteman, 2003). Different subtypes of malignant melanomas show also a significant genetic heterogeneity: CMM arising in sites intermittently exposed to the sun harbor BRAF and/or N-ras mutations more frequently; while malignant melanomas on chronically sun exposed skin (LMM) and ALM show more frequent c-Kit mutations (Curtin 2006). While cutaneous malignant melanoma, when diagnosed and treated in an early stage (pure radial or early invasive growth phase) has a very good prognosis and can still be treated in a curative way via surgery, metastatic melanoma decreases the chances of survival markedly, because of the inherent resistance of the melanoma cells to classical cytotoxic chemotherapy. The most important predictor of progression of malignant melanoma and survival is Breslow thickness of the primary tumor at diagnosis. Breslow thickness is a histological characteristic of the tumor and refers to the thickness of the tumor, measured as the distance between the granular layer of the epidermis and the deepest tumor cell in millimetres. According to the recent final version of the 2009 American Joint Committee of Cancer (AJCC) melanoma staging and classification, primary tumor ulceration and primary tumor mitotic rate are considered as independent prognostic factors for survival and have been included in tumor staging (Balch 2009). For instance, patients with a melanoma equal or less than 1 mm thickness, without ulceration or mitosis and without nodal or distant metastasis (T1aN0M0, stage IA) have a very good prognosis, reflected by a five and ten year survival of respectively 97 and 93%, whereas patients with an ulcerated melanoma of over 4 mm thickness, but without nodal or distant metastasis at diagnosis (T4bN0M0) have a 5 and 10 year survival of 53% and 39% respectively. Once distant metastasis occurs, the prognosis is bad, i.e. a patient with distant metastatic melanoma to the viscera (stage IV, M1c) has a 1 year survival of 33% (Balch 2009). Other known predictive prognostic factors are presence and distribution of tumor infiltrating lymphocytes, tumor site, sex, and social deprivation. (Balch, 2009; Newton Bishop 2009).

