### 2.2. Secondary objective

Secondary efficacy endpoints are:

- Melanoma subtype, as assessed clinically and histologically
- Melanoma site, as clinically recorded
- 25(OH)D3 serum levels at diagnosis and at 6 months intervals
- Stage of melanoma patient at diagnosis according to the 2009 AJCC Melanoma staging and classification

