## **7. STATISTICAL METHODS**

### **7.1. Sample Size**

Approximately 500 patients for the treatment group and for the control group are required. Assuming similar times to relapse as retrospectively observed at the University hospital Leuven, 3 year of recruitment and a total study duration of 3.5 years, 500 patients will have 90% power to detect a hazard ratio of 0.40 in favour of the vitamin D supplemented arm by means of Cox proportional hazards model stratified for time since diagnosis (3 strata: 0, 6 or 12 months ago). The hazard ratio of 0.40 is in correspondence with the intermediate effect size that was reported by Newton-Bishop et al (2009) and a potential increase in VD serum levels of 70 nmol/L which is 80% of the observed effect in a study with CPOD patients (Lehouck et al, 2012). It is anticipated that no patient will be lost for follow-up.

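### The primary Cox model omits melanoma stage, which is prognostic and known before randomisation; the test is valid but gives up some power that a sensitivity analysis cannot restore

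*Combined protocol and SAP*

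**What the plan says.** Section 7.2 states that "relapse-free survival will be compared between the two treatment groups by means of a Cox proportional hazards model stratified for time since diagnosis". Section 7.1 bases the power on the same model: "by means of Cox proportional hazards model stratified for time since diagnosis". Randomisation is stratified on the same single factor (sections 3.2 and 4.2).

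Section 7 uses stage only once: "The potential correlation between VDR immunoreactivity and stage at diagnosis will be assessed by means of a Kruskal Wallice test". No relapse analysis names it. Covariate adjustment appears only as a sensitivity analysis: "A correction for other baseline covariates like gender, age and" baseline vitamin D level. That list is open-ended, and section 7.2 adds: "Full details of the statistical analyses will be described in a statistical analysis plan which will be finalized before database lock". No separate SAP text is in the documents.

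Elsewhere the protocol treats stage and its components as major determinants of outcome. Section 1.1 says: "The most important predictor of progression of malignant melanoma and survival is Breslow thickness of the primary tumor at diagnosis". It also says that "primary tumor ulceration and primary tumor mitotic rate are considered as independent prognostic factors for survival and have been included in tumor staging". Section 3.1 leaves out stage IA because relapse is so rare there. Section 4.2 places staging before consent, screening and randomisation, and section 3.3.2 makes stage IB to III an eligibility criterion. Section 2.2 lists as a secondary endpoint: "Stage of melanoma patient at diagnosis according to the 2009 AJCC Melanoma staging and classification".

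**The concern.** A baseline factor that the protocol regards as strongly prognostic, and that should be known for every patient before allocation, plays no part in the primary comparison. Two things follow.

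- **Power.** When patients with very different relapse risks are pooled, the Cox hazard ratio is pulled towards 1 and the test loses some power. Adjusting in a sensitivity analysis does not help, because that analysis does not decide the primary result.
- **Chance imbalance.** Stage is not a stratification factor, so the arms will differ somewhat in stage. The planned hazard ratio carries that difference in whichever direction it falls. The imbalance is fixed among the 500 randomised, so more relapses do not shrink it. If it is noticed after unblinding, adding stage then would look data-driven.

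**Working it through.** **Inputs from the protocol.** 500 patients in total (sections 3.1, 3.3.1), 1:1 allocation, HR 0.40, 90% power, 3 years' recruitment, 3.5 years in total, no loss to follow-up (section 7.1). Significance level, control relapse rate, stage shares and relapse hazards by stage are not given.

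**The plan's own figure.** With two-sided 5% assumed, Schoenfeld's formula gives 4 × (1.960 + 1.282)² / (ln 0.40)² ≈ 50.1, so 51 relapses. With exponential relapse and follow-up uniform on 0.5 to 3.5 years, 51 relapses among 500 imply a control hazard of about 0.079 per year (21% relapsed at 3 years). The 90% is plausible, but it cannot be verified without the relapse rate and significance level.

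**Assumed stage mixes.**

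| Mix | Shares IB/II/III | Relative hazards |
|---|---|---|
| A | 45/35/20% | 1:2:4 |
| B | 45/35/20% | 1:3:7 |
| C | 60/25/15% | 1:3:7 |
| D | 45/35/20% | 1:5:20 |

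**Simulation.** 500 patients, permuted blocks of 4 within three time strata (168/168/164), stage independent of stratum, exponential times. The baseline hazard is set for 51 relapses at HR 0.40 on the section 7.1 timeline and kept for the longer timelines. Both models are fitted to the same data (stratified Cox, Wald test), 8,000 trials per cell.

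Rejection rate, planned → with stage:

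| Setting | A | B | C | D |
|---|---|---|---|---|
| HR 0.40, section 7.1 timeline, about 51 events | 0.866→0.876 | 0.853→0.874 | 0.849→0.877 | 0.821→0.874 |
| HR 0.40, enrolment fall 2012 to fall 2023, 70-72 events | 0.954→0.963 | 0.947→0.964 | 0.945→0.965 | 0.914→0.957 |
| HR 0.40, 3.5 years for all, 83-85 events | 0.979→0.984 | 0.970→0.979 | 0.971→0.983 | 0.949→0.980 |
| HR 0.50, section 7.1 timeline | 0.676→0.691 | 0.670→0.703 | 0.646→0.684 | 0.627→0.698 |
| HR 0.60, section 7.1 timeline | 0.458→0.472 | 0.444→0.474 | 0.427→0.464 | 0.397→0.464 |
| HR 0.60, 3.5 years for all | 0.677→0.706 | 0.640→0.692 | 0.620→0.688 | 0.556→0.679 |
| HR 1.0, section 7.1 timeline | 0.046→0.051 | 0.050→0.051 | 0.048→0.054 | 0.045→0.050 |

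At the design point the gain is 1.0/2.1/2.8/5.3 points (SE 0.2-0.3). The squared ratio of mean Z is 1.037/1.071/1.087/1.165, so the planned model would need about 4-17% more events for the same power. Over both timelines under no effect, type I error is 4.4-5.0% as planned and 4.7-5.4% with stage (SE about 0.25).

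**Chance imbalance.** Take the log ratio of mean stage hazard between arms of 250. Its SD is about √(CV² × 2/250), where CV² is the squared coefficient of variation of the stage hazard.

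- Mix A: the mean hazard is 0.45 + 0.70 + 0.80 = 1.95 and the mean square is 0.45 + 1.40 + 3.20 = 5.05. So CV² = (5.05 − 3.80)/3.80 = 0.33 and SD = 0.051.
- A 10% shift is ln 1.10 = 0.095, or 1.86 SD, which is exceeded in either direction in about 6% of randomisations.
- The event count does not enter. Simulated frequencies of at least 10% are 6/16/23/35%, and of at least 20% are 0/1/2/7%.

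Median estimated HR (true HR 0.40, about 51 events; deciles of 800 trials):

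| | A | B | C | D |
|---|---|---|---|---|
| Planned, all trials | 0.403 | 0.409 | 0.415 | 0.429 |
| Planned, decile most adverse to vitamin D | 0.435 | 0.471 | 0.467 | 0.509 |
| Planned, decile most favourable | 0.374 | 0.368 | 0.366 | 0.357 |
| With stage, adverse decile | 0.392 | 0.399 | 0.394 | 0.397 |
| With stage, favourable decile | 0.398 | 0.399 | 0.403 | 0.399 |

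On average the imbalance accounts for 3-11% of the variance of the planned log HR at 51 events and 4-17% at 83-85.

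**Robustness at HR 0.40, about 51 events.** If a quarter of true stage III is recorded as IB or II, the gain is 0.8/1.3/2.0/4.3 points; if half, 0.4/0.7/1.5/2.7. If stage has no prognostic value, power is 0.8799 planned and 0.8798 with stage, so there is no measurable cost. A separately coded simulation (shares 50/30/20%) gave 87.4→88.2% for hazards 1:2:4, 88.4→89.5% for 1:3:6 and 86.1→88.5% for 1:4:10.

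**The case against.** The planned model is internally consistent: the same factor serves for randomisation, power and analysis, and the test keeps its level. At the protocol's own HR of 0.40 the gain in mixes A to C is only 1-3 points, and about 1 point with 3.5 years of follow-up for all, where planned power is already 97-98%. The larger gains need HR 0.50 or 0.60, or mix D, and none of these is in the documents. All of this stands and limits the point to efficiency.

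Section 7.1 does not say whether 0.40 is conditional on stage. If it is marginal, adjustment is a bonus rather than a repair. Even with stage not prognostic, simulated power is 88%, so about 2 points of the gap to 90% have nothing to do with stage. That also stands.

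Chance imbalance is already part of the sampling error. With SE about √(4/51) = 0.28, a 10% shift (0.095) is about a third of a standard error, and the outer deciles are selected extremes. True, but adjustment removes this part of the error at no measurable cost.

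The covariate list is open and the SAP is still to come. However, section 7.2 places covariate correction among the sensitivity analyses, so adding stage to that list would not change the primary test.

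Finally, Breslow thickness is named as the strongest single predictor, and three stage groups pool all of stage II. Adjustment for thickness or ulceration was not compared, and non-proportional stage effects were not simulated. Stage is proposed because it is needed for eligibility, not because it is shown to be the best covariate.

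**Conclusion.** The point holds as an efficiency point that should be acted on, not as an error in the planned test. Omitting stage leaves type I error at about 5%. It costs about 1-3 points of power at the design point under moderate gradients and 5 points under the steep one. If the true HR is 0.50 or 0.60, the cost is 1.4-12.3 points across the section 7.1 timeline and 3.5 years for all. It also leaves the hazard ratio open to chance stage imbalance, which is small on average but worth 10% or more in a minority of randomisations. These sizes depend on assumed stage shares, proportional stage hazards, exponential relapse times and a two-sided 5% test. Mix D should not be read as typical.

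**What to change.** Pre-specify AJCC 2009 stage (IB / II / III, two terms) as a covariate in the primary Cox model, and keep time since diagnosis as the stratification factor.

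- Use the stage recorded at screening for eligibility, whether or not a sentinel node biopsy was done, with no re-staging after randomisation.
- If that stage is missing and blinded staff cannot recover it from source, code the most frequent stage so that everyone stays in the intention-to-treat analysis, and report how many.
- Keep the currently planned model as a named sensitivity analysis, and state that the primary hazard ratio is conditional on stage.
- Make the change while those responsible are blinded to relapse by arm. The DSMB and its statistician see unblinded relapse comparisons (section 4.3.7) and should take no part. Because the DSMB communicates directly with the Executive Committee, which maintains the protocol (sections 8.2.1 and 8.2.2), the amendment should record that its authors have seen no such comparison.

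The cost is small but not zero. The model is written into sections 7.1 and 7.2, so a protocol amendment is needed as well as SAP text, and it may count as substantial and require assessment by the authorities and ethics committees (section 8.1). Randomisation does not change and no new data are collected.

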### **3. OVERALL DESIGN AND PLAN OF THE STUDY**

#### **3.1. Overview of study flow**

To investigate whether vitamin D supplementation after diagnosis affects malignant melanoma outcome (primary endpoint relapse free survival), stage IB-III patients will be enrolled from fall 2012 to fall 2023. Stage IA patients will not be included in the study because they only have a very small chance to relapse. This double-blind randomized study will comprise 500 patients (stage IB-III). This patient cohort will be randomized in a 1:1 ratio to vitamin D supplementation or placebo. We will also assess the expression of the Vitamin D Receptor (VDR) expression in the primary tumor. A blood sample will be taken for DNA analysis (genetic variability in the vitamin D pathway). We will check 25(OH)D3 serum levels both at diagnosis, and every 6 months until the end of the study. This patient cohort will exist of 3 subgroups (patients diagnosed within 6 or 12 months before start of the study and newly diagnosed patients). Inclusion of previously diagnosed patients will allow us to assess whether delayed supplementation has a similar effect on the relapse free survival rate as immediate supplementation after surgery of the tumor.

In this randomized vitamin D supplemented placebo-controlled trial (both arms), we will assess whether vitamin D supplementation in the follow up period after diagnosis has a protective effect on relapse (primary endpoint) of the malignant melanoma and whether this protective effect correlates with the vitamin D receptor immunoreactivity in the primary tumor.

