### **3.2. Justification of study design**

A previous study has demonstrated the association of higher 25-hydroxyvitamin D3 serum levels with lower Breslow thickness of the tumor at diagnosis (Newton-Bishop, 2009), suggesting a protective effect of higher vitamin D levels on disease progression of cutaneous malignant melanoma.

To further proof the protective effect of Vitamin D supplementation on melanoma disease progression, this study will give high dose vitamin D supplementation to the melanoma patients after surgery of the primary tumor ( which is the current best standard of care), in a placebo controlled and double blind way. The effect of high dose vitamin D supplementation in double blind placebo controlled way will be primarily tested on relapse free survival.

Patients will be randomly assigned in a 1:1 ratio to receive a monthly oral dose of 100 000 IU of vitamin D (1ml of D-Cure) or placebo (1 ml of olive oil). A block randomization method stratified on time of diagnosis (newly diagnosed, 0-6 months or 6-12 months before start of the study) will be used to overcome seasonal influences on baseline characteristics.

We will also assess the expression of the Vitamin D Receptor (VDR) expression in the primary tumor. A blood sample will be taken for DNA analysis (genetic variability in the vitamin D pathway). We will check 25(OH)D3 serum levels both at diagnosis, and every 6 months until the end of the study. If the level of 25(OH)D3 serum is above 80 ng/ml, study drug will be interrupted and during drug free interval the 25(OH)D3 serum levels will be checked every 3 months. When serum 25(OH)D3 falls below 50 ng/ml, study drug is restarted

The patient cohort will exist of 3 subgroups (patients diagnosed within 6 or 12 months before start of the study and newly diagnosed patients). Inclusion of previously diagnosed patients will allow us to assess whether delayed supplementation has a similar effect on the relapse free survival rate as immediate supplementation after surgery of the tumor.

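### The check for stratum dependence in 7.2 cannot show that delayed supplementation has a similar effect to immediate supplementation, and stratum results are promised only if that check is positive

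*Combined protocol and SAP*

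**What the plan says.** Section 3.1 gives a purpose for enrolling patients diagnosed up to 12 months earlier: to "assess whether delayed supplementation has a similar effect on the relapse free survival rate as immediate supplementation after surgery of the tumor". Section 3.2 repeats it: "Inclusion of previously diagnosed patients will allow us to assess whether delayed supplementation has a similar effect". Randomisation is stratified on time since diagnosis in three strata (3.2 and 4.2).

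Section 7.2 makes a Cox model stratified on the same factor the primary analysis, then adds: "It will be verified whether the treatment effect is stratum dependent. If so, the strata will be analysed separately". It does not name the test, its degrees of freedom or its level. It gives no interval or margin for the difference between strata and does not say what a negative check would mean. Full details are deferred to a statistical analysis plan to be finalised before database lock, which is not in the text available.

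Section 7.1 sizes the trial for the overall comparison only: "500 patients will have 90% power to detect a hazard ratio of 0.40 in favour of the vitamin D supplemented arm". It states no alpha, no relapse rate, no number of events and no power for any comparison between strata.

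**The concern.** Asking whether two effects are similar is an equivalence-type question. A check for a difference answers it only when the check is positive, because a non-significant interaction may simply reflect few events. As 7.2 is written, a negative check leaves one pooled hazard ratio. The reader is promised neither stratum estimates nor an interval showing how large a difference remains compatible with the data.

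What is at stake is the message for patients who start 6 to 12 months after diagnosis. If the strata are never shown separately, the absence of a detected difference could be taken as support for a similar effect when the data hardly bear on the question. The primary analysis itself is not affected.

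**Working it through.** **Inputs from the protocol.** HR 0.40, 90% power, 500 patients, 3 years of recruitment, 3.5 years in total and no loss to follow-up (7.1); 1:1 allocation and three strata (3.1, 3.2).

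**Assumptions, because the protocol is silent.** Two-sided 5%; equal strata at first, then 20-80% newly diagnosed; constant hazard.

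**Step 1. The plan's own figure.** The 90% cannot be reproduced directly, since alpha, relapse rate and events are not given. The events it implies can be derived, with ln(0.40) = -0.916 and its square 0.840:
- Schoenfeld: 4 × (1.960 + 1.282)² / 0.840 = 50.06, so 51 events.
- Freedman: (1.4/0.6)² × (1.960 + 1.282)² = 57.2, so 58 events.

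**Step 2. Missing a complete loss of effect, 1 df.** Suppose the true HR is 0.40 in newly diagnosed patients and 1.0 in both delayed strata, a ratio of HRs of 2.5. With D events in equal strata and variance 4/events for each log HR, the immediate-versus-delayed contrast has variance 4/(D/3) + 4/(2D/3) = 18/D.
- D = 51: SE = √(18/51) = 0.594; 0.916/0.594 = 1.54; power = Φ(1.54 - 1.96) = 0.34; missed in 66%.
- D = 58: SE = 0.557; 0.916/0.557 = 1.64; power 0.38; missed in 62%.

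**Step 3. The same with a 2-df heterogeneity test.** The noncentrality is 0.840 × (D/12) × (2/3).
- D = 51: 2.38, missed in 74%.
- D = 58: 2.71, missed in 71%.

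**Step 4. What an apparently perfect result would show.** With an observed ratio of HRs of exactly 1, the 95% CI is exp(±1.96 × SE).
- D = 51: 0.31 to 3.20.
- D = 58: 0.34 to 2.98.

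Both include 2.5, the complete loss of a 0.40 effect.

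**Step 5. Other readings.** Solving for the control hazard that gives 51 or 58 events at HR 0.40 in 500 patients followed for 0.5 to 3.5 years yields 0.079 or 0.090 per year (21% or 24% relapse at 3 years). Events then arise under the loss-of-effect scenario, with variance 1/(control events) + 1/(treated events) per stratum. The ranges cover 1 and 2 df and 20-80% newly diagnosed.

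| Reading | Complete loss missed |
|---|---|
| 500 patients, 3 + 0.5 years (7.1) | 57-82% |
| 500 patients, 3.5 years each (the maximum in 4.3.8) | 36-71% |
| 1000 patients, 3 + 0.5 years | 28-67% |

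The last row takes literally the 7.1 sentence "Approximately 500 patients for the treatment group and for the control group are required", keeping the hazard solved for 500. Sections 3.1 and 3.3.1 give 500 in total.

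**Step 6. Partial loss.** If the delayed HR is 0.70, the ratio is 0.70/0.40 = 1.75. The 1-df contrast misses it in 84% of trials at 51 events and still in 73% at 102 events.

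**Step 7. Events needed.** For the 1-df contrast with equal strata, 18 × (1.960 + z)² / 0.840 gives 169 events for 80% power (z = 0.842) and 226 for 90% (z = 1.282).

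**The case against.** **The plan states no such rule.** A reader might infer that 7.2 makes similarity the default conclusion whenever an interaction test is not significant. The text does not say so. It names no test and no p-value rule, and keeping a common effect in a stratified Cox model when no heterogeneity is seen is ordinary practice. This stands: the misreading is a risk left open.

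**A missed interaction is not a false claim of benefit.** A reader might also infer that the trial would usually report delayed supplementation to work as well as immediate when it does nothing. That would need a significant pooled benefit as well as a missed interaction. Simulation of HR 0.40/1.0/1.0 in 500 patients used a control hazard of 0.077 per year (about 50 events under 7.1) and a 2-df test. It covered equal or 60/20/20 strata, with 0.5-3.5 or 3.5 years of follow-up. A pooled benefit occurred in about 9-54% of trials, and both together in about 8-31%. The stronger reading fails.

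**The comparison is minor and detail is deferred.** It is not among the endpoints in 2.1 and 2.2 or the two questions in 1.2, and low power for such a comparison is common. The later analysis plan may contain stratum estimates. Both points are fair and limit the weight of the concern. However, 3.1 and 3.2 give the comparison as a reason for the design, and 7.2 mentions no similarity criterion among what it defers.

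**The miss rates rest on assumptions.** This also stands. With longer follow-up or 1000 patients, some readings fall below one half, so no single figure is a floor.

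**Conclusion.** The concern holds in limited form. The protocol says it will assess similarity between delayed and immediate supplementation, describes only an unspecified check for a difference, and makes stratum results conditional on that check being positive. A negative check would be weak evidence. At the 51-58 events implied by 7.1, it would miss complete loss of the effect in about 62-66% (1 df) to 71-74% (2 df) of trials. These figures assume a two-sided 5% level and equal strata. Across the other readings of follow-up, sample size and stratum sizes the range is about 28-82%. None of those readings supplies a criterion for similarity.

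The documents do not support the claim that a negative result will be reported as similarity, or that a misleading benefit in delayed patients is the usual outcome. What they support is that non-significance could be misread and that the plan does nothing to prevent it. The change is worth making because it is almost free and sets what the trial can say about delay.

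**What to change.** In 7.2, replace the conditional split with estimation that is always reported. Fit the Cox model, stratified on time since diagnosis, with a treatment-by-stratum term. Whatever the p-value, give the HR in each stratum and the ratios of HRs (each delayed stratum against newly diagnosed) with 95% CIs. State that a non-significant check is not evidence of a similar effect.

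In 3.1 and 3.2, describe the aim as an exploratory estimate of how the treatment effect varies with delay. A formal equivalence margin is optional and is not needed for this correction.

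The cost is a few sentences in the protocol and analysis plan and one model term, with no extra patients or data. The trial gives up a similarity claim that it could not have supported.
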